3.5 Study Procedures

3.5.1 Study Preparation

Project Initiation: Submission of materials to the Clinical Research Center; project initiation following scientific review approval.

Ethical Approval: Submission of materials to the Ethics Committee for review. Ethical approval to be obtained to ensure compliance with ethical standards.

Resource Preparation: Preparation of neuromodulation equipment and associated technologies. Recruitment and training of research personnel to ensure familiarity with study procedures and operational protocols.

3.5.2 Participant Recruitment

Recruitment announcements will be published to disseminate information regarding the study objectives and eligibility criteria.

3.5.3 Informed Consent

Written informed consent will be obtained from all eligible participants prior to enrollment.

3.5.4 Screening Phase

Medical history documentation will be collected, including sex, age, medical record number, history of present illness, and past medical history. The following examinations will be completed: blood biochemistry, complete blood count, coagulation function, and neuroimaging (cranial CT/MRI). Baseline clinical assessments will be performed, including the Fugl-Meyer Assessment, Brunnstrom staging, and Modified Ashworth Scale grading.

3.5.5 Group Allocation

A total of 60 patients with hemiplegic upper limb dysfunction during the recovery phase of stroke, undergoing inpatient rehabilitation at the Department of Rehabilitation Medicine, Taizhou People's Hospital, will be randomly allocated into a neuromodulation group and a

control group (n = 30 per group) using a random number table. All participants in both groups will receive conventional pharmacological therapy (including antiplatelet aggregation agents, neurotrophic agents, circulatory improvement agents, plaque stabilizers, antihyperglycemic/antihypertensive agents, and supportive therapy) and standard rehabilitation interventions (physical therapy and occupational therapy). The neuromodulation group will receive one week of transcranial focused ultrasound stimulation in addition to conventional treatment. The control group will undergo the same assessment and procedural steps as the experimental group but will receive sham stimulation.

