CLINICAL PROTOCOL

Transcranial Focused Ultrasound Neuromodulation for Post-Stroke Motor Dysfunction

Sponsoring Institution: Taizhou People's Hospital

Principal Investigator / Department: [name] / Department of Rehabilitation Medicine

Study Period: March 2026 – March 2028

Version: 2.0

Version Date: April 27, 2026

Protocol Synopsis

Project Title	Clinical Protocol for Transcranial Focused Ultrasound Neuromodulation in Post-Stroke Motor Dysfunction
Study Objectives	This study aims to evaluate how transcranial focused ultrasound (tFUS) technology promotes the remodeling of damaged neural networks and functional recovery by activating or inhibiting neural activity in specific brain regions, integrating electroencephalography (EEG) and magnetic resonance imaging (MRI) signal analyses. The primary goals are to improve motor ability and cognitive function, reduce long-term disability, and enhance quality of life. Additionally, this study seeks to optimize stimulation parameters to achieve maximal rehabilitative outcomes and to elucidate the potential mechanisms underlying neuroprotection and functional reconstruction following stroke.
Study Design	This study is a randomized, controlled, single-center trial.
Sample Size	60 participants
Participant Selection	Inclusion Criteria: (1) Patients with a confirmed imaging diagnosis of first-ever ischemic stroke; (2) Unilateral limb motor involvement; (3) Modified Ashworth Scale (MAS) grade ≤ 3 for the upper extremity, Brunnstrom stage II–V, and upper extremity Fugl-Meyer Assessment (FMA-UE) score between 15 and 60 (inclusive); (4) Age 18–75 years, onset within 21 days to 6 months, in the subacute or recovery phase; (5) Stable vital signs, no consciousness impairment, informed consent provided, ability to cooperate with clinical assessments, and approval obtained from the institutional ethics committee. Exclusion Criteria: (1) Contraindications to MRI; (2) Infarction involving the thalamus; (3) Risk of intracranial hemorrhage; (4) Presence of intracranial metallic foreign bodies, cardiac pacemakers, or cochlear implants; (5) Unstable medical condition, severe cognitive impairment or psychiatric disorders rendering the patient unable to comprehend the study or cooperate with assessments; (6) Conditions affecting limb motor function, including fractures, joint contractures, or severe limb spasticity; (7) Current use of medications that alter cortical excitability.

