3.1 Study Design

This study is a randomized, controlled, single-center trial.

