3.2 Sample Size

Participants will be recruited from inpatients of the Department of Rehabilitation Medicine. Based on preliminary literature review and the current inpatient volume of our department, the provisional sample size is set at $n = 60$, with 30 participants allocated to each group.

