3.7 Control Group Intervention

The control group receives sham stimulation during the neuromodulation phase. All procedural steps are identical to those of the experimental group, including neuronavigation positioning, application of coupling gel, and all other preparatory procedures; however, ultrasound stimulation is not activated. Participants in the control group wear bone-conduction headphones to simulate and counteract acoustic confounding. Group allocation information is blinded to participants.

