November 2026 – August 2027: Continued case recruitment, statistical analysis of accumulated data, and objective evaluation of outcome measures across groups.

September 2027 – December 2027: Participation in provincial and national rehabilitation conferences, with preliminary findings presented for peer review and scholarly exchange.

January 2028 – February 2028: Continuation of clinical data collection, synthesis of completed research, comprehensive data analysis, and evaluation of study outcomes.

March 2028: Project completion, manuscript preparation, and publication.

9. Research Team

Name	Title / Specialty	Responsibilities
[name]	Chief Physician	Quality Control
[name]	Chief Physician	Data Analysis
[name]	Associate Chief Physician	Case Recruitment
[name]	Chief Physician	Data Analysis
[name]	Associate Chief Physician	Manuscript Preparation
[name]	Attending Physician	Case Recruitment
[name]	Attending Physician	Case Recruitment
[name]	Attending Physician	Case Recruitment
[name]	Attending Physician	Case Recruitment
[name]	Attending Physician	Rehabilitation Assessment
[name]	Senior Therapist	Rehabilitation Assessment

10. References

- [1] GBD 2021 Causes of Death Collaborators. Global burden of 288 causes of death and life expectancy decomposition in 204 countries and territories and 811 subnational locations, 1990–2021: a systematic analysis for the Global Burden of Disease Study 2021. *Lancet*. 2024;403(10440):2100.

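### Section 3.5.5 fixes 30 per group by a random number table but states neither the restriction that gives that split nor how the list is concealed from recruiting staff

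*Protocol*

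**What the plan says.** Section 3.1 describes the design in one sentence: "This study is a randomized, controlled, single-center trial". Section 3.2 sets the total at 60, "with 30 participants allocated to each group". Section 3.5.5 repeats the split and names the method: patients go to a neuromodulation group and a "control group (n = 30 per group) using a random number table". No block size, restriction rule, list holder or time of disclosure is given.

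On masking, section 3.7 says "Group allocation information is blinded to participants" and mentions no one else. In the sham arm every preparatory step is carried out but "ultrasound stimulation is not activated".

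Section 8 gives one period, November 2026 to August 2027, to "Continued case recruitment, statistical analysis of accumulated data, and objective evaluation of outcome measures across groups". Section 9 lists eleven team roles: five for case recruitment, two for data analysis, two for rehabilitation assessment, one for quality control and one for the manuscript. None is described as holding the allocation list.

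The synopsis (Statistical Methods) compares the groups by independent-samples t-tests, with non-parametric tests for non-normal data. Section 3.4 admits patients with "onset within 21 days to 6 months, in the subacute or recovery phase" and with FMA-UE scores from 15 to 60.

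**The concern.** An exact 30/30 split needs some restriction on the sequence, and any restriction makes later assignments partly predictable to someone who knows the earlier ones. Concealment normally closes that route, and the protocol describes none. It has to be in force before the first patient is entered, so it cannot wait for a statistical analysis plan.

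Several features of this trial make the gap matter. Recruitment is from one department. Whoever runs the device can tell real from sham stimulation. Group comparisons are planned while patients are still being entered. Some exclusions rest on judgement without a stated threshold (haemorrhage risk, medical instability, severity of spasticity). A recruiter who expects a given arm could therefore delay or decline a patient without breaking any written rule. The arms would then differ for reasons other than treatment, and adjustment for measured covariates could not be relied on to remove the difference.

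**Working it through.** **Inputs.** N = 60 and 30 per arm (sections 3.2 and 3.5.5). 30 + 30 = 60, so the two sections agree. The protocol gives no restriction rule, so the calculation takes the most natural one that guarantees the stated split: a single random permutation of 30 + 30 entries. The second assumption is that the guesser knows every past assignment. The protocol does not say that recruiters do; this is the case to be sized.

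**Step 1. Best guess at one position.** After k patients, a of them in arm A, the guesser names the arm with more places left:

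P(correct at position k + 1) = Σₐ [C(30, a) · C(30, k − a) / C(60, k)] × max(30 − a, 30 − k + a) / (60 − k)

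**Step 2. Sum over 60 positions.** The sum has the closed form 30 + (4³⁰ / C(60, 30) − 1) / 2. Since 4³⁰ / C(60, 30) = 9.749, this is 30 + 8.749 / 2 = 34.37 correct guesses, and 34.37 / 60 = 57%. Chance gives 30 / 60 = 50%, so the knowledge is worth about 4.4 extra correct guesses.

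**Step 3. Where the gain falls.**

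| Patients | Expected correct | Share |
|---|---|---|
| First 45 | 24.36 | 54% |
| Last 15 | 10.01 | 67% |
| All 60 | 34.37 | 57% |

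The expected number of patients at the end whose arm is fully determined, because the other arm is full, is 2 × 30 / 31 = 1.9.

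**Step 4. Would blocking alone cure it?** Take fixed blocks of 4 whose size is known. The chances of a correct guess at the four positions are 1/2, 2/3, 2/3 and 1, which sum to 2.833. Over 15 blocks that is 42.5 of 60, or 71%, worse than the single list. Blocking helps only if sizes vary, are undisclosed and the list is concealed.

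**Step 5. Range by what recruiters know.**

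| Recruiters' knowledge | Best guess correct |
|---|---|
| Nothing | 50% |
| All past assignments, single 30 + 30 list | 57% |
| The list itself | 100% |

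The protocol does not say which row applies.

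**Step 6. Chance imbalance, for the analysis model.** At 30 per arm the standard error of a standardised baseline difference is √(1/30 + 1/30) = 0.258. The chance that it exceeds 0.3 SD in either direction is 2 × (1 − Φ(0.3 / 0.258)) = 0.245. This applies to any baseline variable left unstratified, including FMA-UE.

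**The case against.** The strongest reply is that a random number table is a source of random digits and not an allocation rule. Section 3.5.5 is naturally read as one list of 30 + 30 drawn up from a table, and that gives 30/30 with certainty. This stands. A reader might infer that the stated method fails to deliver equal arms, because reading the table patient by patient gives exactly 30/30 with probability only C(60, 30) / 2⁶⁰ = 0.103, or that closing a full arm would leave on average 6.2 assignments fully determined. The protocol states neither procedure, so those figures do not describe this trial.

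A second reply is that silence on concealment is not a statement that allocation is open. This also stands. A reader might infer from section 8 that recruiters know the running count per arm, but it does not say who makes the comparisons or who sees them. Section 9 lists recruitment and data analysis as separate roles, and with names removed no overlap can be shown. Even with all past assignments known, the gain in Step 2 is modest and falls mainly on the last quarter of patients.

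A third reply is that sections 3.5.3 to 3.5.5 already run from consent through baseline scales to allocation. That is partly right. However, the pre-test with MRI and EEG appears only in section 3.6, and nothing ties disclosure of the arm to its completion.

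None of this supplies the missing safeguard. Concealment is part of the allocation procedure, which section 3.5.5 sets out to describe.

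**Conclusion.** The point holds as a gap in the allocation procedure. The protocol fixes equal arms and a source of randomness, but neither the restriction nor any concealment from recruiters. With blinding stated for participants only, a device operator who can know the arm, and group comparisons during accrual, selection at entry cannot be ruled out.

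The 57% overall and 67% over the last 15 patients rest on two assumptions: a single 30 + 30 list and full knowledge of past assignments. Predictability would be nil with proper concealment and complete if the list were open. The documents do not show that selection bias will occur.

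A reader might also infer that unstratified allocation is an error, given the range of time since onset. The documents do not support that. Unstratified allocation is legitimate in a single-centre trial of 60, chance imbalance is already reflected in the standard error, and the protocol gives no figure for how recovery varies with time since onset. Stratification is an optional design choice and has no bearing on foreseeability.

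The change should be made before allocation begins, which section 8 places in June 2026.

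**What to change.** 1. In section 3.5.5, replace the reference to a random number table with a computer-generated 1:1 list in permuted blocks of varying size, the sizes not disclosed to recruiters, operators or assessors.
2. State that the list is prepared and held by an existing staff member with no part in recruitment, assessment or analysis. Each assignment is released (sequentially numbered opaque envelope or password-protected file) only after consent and the pre-test are complete.
3. In sections 3.7 and 8, state that allocation and by-arm results are kept from recruiting staff until enrolment ends.
4. In the synopsis, replace the unadjusted t-test for FMA-UE with a model that has baseline FMA-UE as a covariate and, if wished, time since onset. Baseline FMA-UE is already collected under section 3.5.4. This deals with chance imbalance in that score; it does not substitute for concealment.
5. Stratifying by time since onset may be added but is not required.

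The cost is a few sentences of protocol text, one list and some time from an existing staff member. The downside is that the final split may be one or two patients off 30/30. The efficiency loss is negligible: even 27/33 keeps 4 × 27 × 33 / 3600 = 99% of the efficiency of equal arms.

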3.6 Neuromodulation Intervention

The transcranial focused ultrasound stimulation device employed in this study is the NeuroFUS DPX-500, equipped with a 4-element transducer array and the BrainSight neuronavigation system. Individualized modeling and target segmentation are performed using high-resolution structural MRI and CT images acquired at baseline. Target planning and neuronavigation are conducted based on intracranial acoustic field simulation. The total stimulation duration is 12 minutes, comprising 480 pulse trains with 0.5 seconds on and 1 second off, yielding a duty cycle of 20%. The intensity at the intracranial target site (after skull attenuation) is uniformly set at 8 W/cm².

Experiments will be conducted in a soundproofed, electromagnetically shielded room free from excessive illumination or reflective surfaces. The facility is equipped with provisions for prompt hair washing and EEG cap cleaning, and is situated within a 10-minute walk to the MRI suite.

The experimental protocol spans one week and comprises three principal phases: pre-test, neuromodulation, and post-test. The pre-test includes cranial MRI acquisition, clinical scale assessment, and EEG data collection. Neuromodulation sessions are administered once daily for a total of five sessions per week, with EEG recordings obtained before, during, and after each stimulation session. The post-test consists of cranial MRI acquisition identical to the pre-test protocol, conducted within two days of completion of all neuromodulation sessions.

The pre-test serves as a baseline measurement and primarily includes neuroimaging acquisition and resting-state/task-state EEG measurements. Neuroimaging acquisition encompasses cranial CT (the most recent CT obtained proximal to onset per admission protocol) and cranial MRI acquired using study-specific sequences, including T1-weighted, T2-weighted, resting-state functional MRI, and diffusion tensor imaging. Pre-test data are also utilized for individualized neuronavigation and acoustic field modeling simulation. This involves deep brain nuclei segmentation based on individual structural images, recording of target coordinates via the neuronavigation system, cranial acoustic parameter analysis using CT and structural images, planning of individualized neuromodulation incidence positions and parameter sequences by setting a uniform in situ target intensity, and concurrent safety testing and thermal simulation.

Five neuromodulation sessions are administered in total. Sessions 2 and 5 involve simultaneous EEG-coupled ultrasound neuromodulation, while Sessions 1, 3, and 4 consist of ultrasound neuromodulation alone. During EEG-coupled sessions, EEG signals are acquired before, during, and after ultrasound stimulation; during standalone sessions, only ultrasound stimulation is delivered without EEG acquisition. Stimulation parameters are maintained at consistent control levels across participants. Based on each individual's

cranial acoustic parameters, the pre-attenuation stimulation intensity is back-calculated to ensure uniform in situ intensity at the target. The spatial-peak temporal-average intensity at the target is maintained below the diagnostic ultrasound safety threshold (720 mW/cm²). The ultrasound stimulation duration is 12 minutes using a 20% duty cycle pulse sequence.

The post-test cranial MRI protocol is identical to the pre-test and is performed within two days of completion of all neuromodulation sessions.

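### A train of 0.5 s on and 1 s off has a 33.3% duty cycle, not 20%, and with the 8 W/cm² unlabelled the 720 mW/cm² limit cannot be checked

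*Protocol*

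**What the plan says.** All the relevant text is in Protocol section 3.6.

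- The opening paragraph gives a 12-minute session made up of "480 pulse trains with 0.5 seconds on and 1 second off, yielding a duty cycle of 20" per cent.
- It then fixes the dose: "The intensity at the intracranial target site (after skull attenuation) is uniformly set at 8 W/cm²". It does not say whether this is a pulse average or a temporal average.
- The paragraph on the five sessions says that "the pre-attenuation stimulation intensity is back-calculated to ensure uniform in situ intensity at the target".
- That paragraph also sets a ceiling: "The spatial-peak temporal-average intensity at the target is maintained below the diagnostic ultrasound safety threshold (720 mW/cm²").
- It repeats the duty figure, now attached to the pulse sequence: "The ultrasound stimulation duration is 12 minutes using a 20% duty cycle pulse sequence".
- Planning for each participant includes "setting a uniform in situ target intensity, and concurrent safety testing and thermal simulation".

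Pulse duration, pulse repetition frequency and the duty inside a train are not given.

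**The concern.** The opening paragraph presents 20% as the result of the on/off timing, and that timing does not give 20%. The paragraph on the sessions attaches the same 20% to the pulse sequence, which may mean the pulses inside each train. These are two different quantities, and the text does not say which is meant.

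This matters because the duty cycle links the target intensity to the protocol's own safety ceiling: temporal average = pulse average × overall duty. With the duty ambiguous and the 8 W/cm² unlabelled, a reader cannot multiply the stated settings out and confirm that they fall below 720 mW/cm². The 8 W/cm² is also the target from which each participant's device output is back-calculated, so the meaning of that number has to be fixed. The duty does not enter that back-calculation. It governs the emission time and the temporal average.

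The number at issue is the dose of the investigational treatment, given in five sessions to recent stroke patients under a protocol that names seizure as a risk (section 4.1).

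**Working it through.** **Inputs (Protocol section 3.6).** 480 trains; 0.5 s on; 1 s off; session of 12 min = 720 s; stated duty 20%; target intensity 8 W/cm² = 8,000 mW/cm²; ceiling 720 mW/cm².

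**1. Session length.** Trains × (on + off) = 480 × 1.5 s = 720 s = 12 min. The stated duration is reproduced, which supports the 1.5 s cycle.

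**2. Duty cycle of that timing.** On/(on + off) = 0.5/1.5 = 33.3%. The stated 20% is not reproduced. The ratio on/off, 0.5/1 = 50%, does not give it either.

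**3. Could one time be a slip?**
- Keep 0.5 s on: 20% needs 2 s off, and 480 × 2.5 s = 20 min.
- Keep 1 s off: 20% needs 0.25 s on, and 480 × 1.25 s = 10 min.
- Keep the 1.5 s cycle: 20% needs 0.3 s on and 1.2 s off, so both stated times would be wrong.

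No change to a single time gives both 20% and 12 min.

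**4. What the ceiling allows.** Assume that 8 W/cm² is a pulse average. Maximum overall duty = 720/8,000 = 9%. With trains on for 33.3% of the time, maximum duty inside a train = 0.09/0.3333 = 27%.

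**5. The possible readings, on the same assumption.** Emission time = overall duty × 720 s. Temporal average = 8,000 mW/cm² × overall duty, taken over the full on/off cycle.

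| Reading | Duty inside train | Overall duty | Emission per session | Temporal average | Multiple of 720 |
|---|---|---|---|---|---|
| 20% is the pulse duty inside trains | 20% | 0.20 × 0.3333 = 6.67% | 48 s | 533 mW/cm² | 0.74 |
| 20% is the overall duty | 0.20/0.3333 = 60% | 20% | 144 s | 1,600 mW/cm² | 2.2 |
| 33.3% is the overall duty | 100% (continuous) | 33.3% | 240 s | 2,667 mW/cm² | 3.7 |

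**6. If 8 W/cm² were already a temporal average**, it would be 8,000/720 = 11.1 times the ceiling whatever the duty.

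**7. Averaging interval.** On the first reading, the average within one 0.5 s train is 8,000 × 0.20 = 1,600 mW/cm². It falls to 533 mW/cm² only when the off time is included. The protocol does not state the interval over which its ceiling applies.

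**The case against.** The strongest reply is that the protocol's own constraints leave one workable reading. The ceiling rules out 8 W/cm² as a temporal average, and it rules out 20% or 33.3% as overall duty. The term pulse trains implies pulses inside each train, and the second mention of 20% refers to the pulse sequence. Nesting 20% inside 33.3% fits every printed number and fails only on the claim that the timing yields 20%. On this view the fault is compressed wording, and patients are protected by the ceiling, the acoustic simulation, the safety testing and the thermal simulation.

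Much of this stands:
- The nested reading is the most plausible.
- The 240 s case is the least plausible, since it needs continuous output within trains. Among readings that keep the stated 20%, emission runs from 48 s to 144 s, a threefold range rather than fivefold.
- The safeguards are real, and exceeding the ceiling would violate the text.

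The argument does not answer the main point, because it assumes that the ceiling is met and infers the settings from that. It therefore cannot show that the stated settings meet the ceiling. It also needs two facts that the protocol does not give, a within-train duty and a pulse-average label, and it contradicts the sentence that derives 20% from the train timing.

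**Conclusion.** The concern holds. The 20% is wrong as written: the stated timing gives 33.3%, and the 12-minute total confirms that timing. Compliance with the 720 mW/cm² ceiling cannot be verified from the text. With 8 W/cm² as a pulse average, which is an assumption, the temporal average is 533, 1,600 or 2,667 mW/cm² depending on what the 20% means, and only the first is below the ceiling. That first figure also assumes averaging over the full on/off cycle.

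This is not a finding that patients would be over-exposed. The error may prove to be one of wording alone. It still has to be corrected before treatment starts, because it sits in the dose of the intervention and bears directly on the protocol's own safety limit.

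**What to change.** Amend section 3.6 before any sonication. Section 8 plans the intervention from June 2026.

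- Give the train timing as 33.3%, and make the two mentions of 20% refer to the same, named quantity.
- State the duty inside a train, with pulse duration and repetition frequency, and the overall duty.
- Label the 8 W/cm², as spatial-peak pulse-average intensity if that is what is meant.
- State the resulting temporal-average intensity and its averaging interval, and show that it is below 720 mW/cm².

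If the nested reading is intended, one sentence is enough for the arithmetic: 20% pulse duty within trains × 33.3% train duty = 6.67% overall duty, and 8 W/cm² × 6.67% = 533 mW/cm² averaged over the full on/off cycle. If 20% is instead the overall duty, the pulse-average intensity would have to be below 720/0.20 = 3,600 mW/cm² (3.6 W/cm²), so the 8 W/cm² would have to change. The clinical and acoustic team must decide which parameter is correct.

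The cost is a protocol wording amendment with ethics committee approval. If the nested reading is confirmed, the treatment itself does not change. No extra patients, visits or procedures are needed.
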